9.3.4 Exploratory Endpoints

Exploratory aims include laxative compliance (weekly pill counts), healthcare resource utilization (per electronic medical record evaluation of emergency room visits, hospitalizations, telephone encounters, and Mychart encounters), and patient preference (as evidenced by patient desire to continue naloxegol optional 12-week extension).

For analysis of differences in weekly pill counts between naloxegol and usual care, we plan to use a Poisson generalized linear mixed effects model to determine the impact of naloxegol on weekly pill counts, over the course of 2 weeks for the initial treatment and cross over phases of the study.

Count of healthcare utilization resource- will be the sum of total utilizations (summed separately for each of the two weeks for initial treatment and cross over phase). Differences in healthcare utilization between the arms will be determined by fitting a Poisson regression model (or negative binomial in the case of over dispersion) of treatment arm on bi-weekly utilization count. We will examine patient preference by calculating a 95% confidence interval for the proportion

of patients who wish to continue the optional 12-week extension.

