Cross-Over	Usual Care: stimulant laxative ± osmotic laxative	Single 25 mg tablet Route: Orally, on an empty stomach 1 hour before breakfast or 2 hours after first meal of the day	Daily, Days 18-31	2 weeks (14 days)
Extension (Optional)	Single 25 mg tablet Route: Orally, on an empty stomach 1 hour before breakfast or 2 hours after first meal of the day	Single 25 mg tablet Route: Orally, on an empty stomach 1 hour before breakfast or 2 hours after first meal of the day	Daily, Days 32-116	12 weeks (84 days)

Wash out: Based on an elimination half-life of 10 hours, a 3-day washout period (50 hours or 5 half lives, approximately 48 hours) will occur before crossover.

Optional 12-week extension: Patients on Arms A and B will have the option to continue on naloxegol at 25 mg daily for an additional 12-week extension phase upon completion of initial and crossover treatment phases.

On Study Days 1, 18, 32, patients will undergo physical exam with vital signs and weight, ECOG performance status, complete blood count, comprehensive metabolic panel, and will receive a new treatment supply. Pill counts and study drug accountability will also be performed.

During initial and crossover treatment periods, patients will complete daily questionnaires and diaries, including the patient study drug diary, patient bowel movement diary, patient medication use diary, BSS, and BPI-sf. Concomitant medications and adverse event data will also be collected daily. All adverse events will be graded according to NCI CTCAE v4.03. Weekly assessments will include patient completion of the PAC-SYM questionnaire. Bi-weekly assessments include patient completion of the PAC-QOL questionnaire. Pill counts will be performed weekly throughout the duration of study, and may be performed via telephone call by a member of the study team if no in-person visit has occurred with the patient during a previous week.

During the optional extension phase, patients will be asked to return to clinic every 28 days for a new supply of naloxegol, return of any unused naloxegol, review of the previous month's study drug diary, pill count and completion of PAC-SYM, PAC-QOL, and BPI-sf. Concomitant medications and adverse event data will continue to be collected daily.

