5.1.13.1 Patient Study Drug Diary

Patients will complete a daily study drug diary (**Appendix D**) during the period of time that they are receiving naloxegol: initial treatment phase for patients randomized to Arm A, crossover treatment phase for those randomized to Arm B; extension phase for all patients who choose to continue receiving naloxegol for an additional 12 weeks following the crossover phase. Participants will be asked to complete this diary even on days when a naloxegol dose was missed. The study drug diary will be reviewed with the patient during each visit to clinic, and a copy will be collected by a member of the study team. This diary will be used in combination with a pill count by the study team to support drug accountability.

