5.3.2 Days 2-7, Days 9-14, Days 19-24 and Days 26-31

- Documentation of concomitant medications, adverse events and serious adverse events
- Naloxegol administration (*Arm A, initial period only; Arm B crossover period only*)
- Patient study drug diary (*Arm A, initial period only; Arm B crossover period only*)
- BPI-sf
- BSS

- Patient medication use diary
- Patient bowel movement diary

5.3.3 Day 8, Day 25

- Documentation of concomitant medications, adverse events and serious adverse events
- Naloxegol administration (*Arm A, initial period only; Arm B crossover period only*)
- Naloxegol pill count (*Arm A, initial period only; Arm B crossover period only, via phone if in-person visit not conducted*)
- Patient study drug pill diary (*Arm A, initial period only; Arm B crossover period only*)
- PAC-SYM
- BPI-sf
- BSS
- Patient medication use diary
- Patient bowel movement diary

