8.1.2 Drug Accountability/Subject Compliance

Records of study medications used, dosages administered, and intervals between visits will be kept during the study. Subjects will be asked to fill out a daily study drug diary while taking naloxegol and bring with them, along with any unused study drug, when they return to clinic every 14 days during the initial and crossover treatment phases, and at each in-person visit during the optional extension phase. A review of the subject-completed study drug diary and pill count will be performed by a member of the study team at each of these visits. In addition, a study team member will contact the patient weekly via telephone to perform pill counts if no in-person visit has occurred with the patient during a previous week.

Final drug accountability will be noted at the completion of the trial. Patients will be asked to return all unused medication at the end of the study.

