Appendix D. Patient Study Drug Diary

Protocol No.	Participant No.	Participant Initials	Treatment Phase
UCSD XXXXXX			

- Please complete this diary on a daily basis. Enter the time you take naloxegol in the appropriate box.
- If you forget to take your dose and it has been less than 2 hours since the missed dose, it should be taken as soon as you remember on the same day. If it has been more than 2 hours since missing a dose, put a line through the box for time taken on that day and do not make up that dose. If you vomit after taking a dose, do not repeat the dose and record that on your diary.
- If you experience any health/medical complaints, please record this information on the back of this diary.

Naloxegol Dose: _____ mg

Number of pills per day: 1

Date:	DAY 1	DAY 2	DAY 3	DAY 4	DAY 5	DAY 6	DAY 7
Naloxegol	Time:						

Date:	DAY 8	DAY 9	DAY 10	DAY 11	DAY 12	DAY 13	DAY 14
Naloxegol	Time:	Time:	Time:	Time:	Time:	Time:	Time:

Please sign at completion of the treatment period and return with pill bottle(s) to the study team.

Patient Signature: _____ Date: _____

Protocol No.	Participant No.	Participant Initials	Treatment Phase
UCSD XXXXXX			

- Please complete this diary on a daily basis. Enter the time you take naloxegol in the appropriate box.
- If you forget to take your dose and it has been less than 2 hours since the missed dose, it should be taken as soon as you remember on the same day. If it has been more than 2 hours since missing a dose, put a line through the box for time taken on that day and do not make up that dose. If you vomit after taking a dose, do not repeat the dose and record that on your diary.
- If you experience any health/medical complaints, please record this information on the back of this diary.

Naloxegol Dose: _____ mg

Number of pills per day: 1

Date:	DAY 15	DAY 16	DAY 17	DAY 18	DAY 19	DAY 20	DAY 21
Naloxegol	Time:						

Date:	DAY 22	DAY 23	DAY 24	DAY 25	DAY 26	DAY 27	DAY 28
Naloxegol	Time:						

Please sign at completion of the treatment period and return with pill bottle(s) to the study team.

Patient Signature: _____ Date: _____

Protocol No.	Participant No.	Participant Initials	Treatment Phase
UCSD XXXXXX			Extension

- Please complete this diary on a daily basis. Enter the time you take naloxegol in the appropriate box.

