- If you forget to take your dose and it has been less than 2 hours since the missed dose, it should be taken as soon as you remember on the same day. If it has been more than 2 hours since missing a dose, put a line through the box for time taken on that day and do not make up that dose. If you vomit after taking a dose, do not repeat the dose and record that on your diary.
- If you experience any health/medical complaints, please record this information on the back of this diary.

Naloxegol Dose: _____ mg

Number of pills per day: 1

Date:	DAY 85	DAY 86	DAY 87	DAY 88	DAY 89	DAY 90	DAY 91
Naloxegol	Time:						
Date:	DAY 92	DAY 93	DAY 94	DAY 95	DAY 96	DAY 97	DAY 98
Naloxegol	Time:						
Date:	DAY 99	DAY 100	DAY 101	DAY 102	DAY 103	DAY 104	DAY 105
Naloxegol	Time:						
Date:	DAY 106	DAY 107	DAY 108	DAY 109	DAY 110	DAY 111	DAY 112
Naloxegol	Time:						

Please sign at completion of the treatment period and return with pill bottle(s) to the study team.

Patient Signature: _____ Date: _____

My next scheduled visit is: _____

HEALTH/MEDICAL COMPLAINTS

Please record all health/medical complaints you have experienced below.

Please describe what you experienced	Date Started	Date Stopped

For UCSD Staff Use Only:

Signature: _____

Date: _____

Pill Count (to be completed by study team):

of capsules returned

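### The planned comparison of weekly pill counts does not measure laxative compliance, whichever products are counted

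*Combined protocol and SAP*

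**What the plan says.** Sections 2.3 and 9.3.4 give laxative compliance as the aim, measured by weekly pill counts. Section 2.4 calls the same endpoint compliance with drug administration. The analysis in 9.3.4 is: "For analysis of differences in weekly pill counts between naloxegol and usual care, we plan to use a Poisson generalized linear mixed effects model". The synopsis repeats it. Neither place mentions an offset, a number of doses due, or a list of products to be counted. Section 9.3.3 places all secondary and exploratory analyses in one Bonferroni-Holm family.

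The documents differ on what is counted:

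- Section 5.3.3 lists "Naloxegol pill count (*Arm A, initial period only; Arm B crossover period only, via phone if in-person visit not conducted".
- Section 5.1.13.1 says of the naloxegol diary: "This diary will be used in combination with a pill count by the study team to support drug accountability". Section 8.1.2 has the same scope: "Subjects will be asked to fill out a daily study drug diary while taking naloxegol".
- The only form with a count field, "Pill Count (to be completed by study team", is the naloxegol diary in Appendix D, which is headed "Number of pills per day: 1". The medication use diary in Appendix E has no such field.
- Section 4.1 is unrestricted: "Pill counts will be performed weekly throughout the duration of study". The pill-count row in the Schedule of Events is not limited to naloxegol either.

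**The concern.** Compliance is the share of due doses that were taken. A raw tablet count has only the numerator. Naloxegol has a fixed number of tablets due. Usual care does not: section 1.1 describes stimulant laxatives that patients titrate themselves, and section 1.3 adds polyethylene glycol, which is dosed in grams and contributes no tablets. Section 4.4 allows rescue bisacodyl on both treatments, and 9.3.4 does not say whether those tablets count.

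At stake is the meaning of one reported result. A significant difference in tablet counts, presented under the heading of compliance, would be read as patients adhering better to one treatment when it may show only that one regimen uses more tablets. A real adherence difference could also be hidden or reversed.

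**Working it through.** The documents give no power, effect size or expected count for this analysis, so there is no planned figure to reproduce. The check takes each reading in turn.

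**Reading 1: only naloxegol is counted.** Under 5.1.13.1, 5.3.3, 8.1.2 and Appendix D, each patient has counts in the naloxegol period and none in the usual-care period. The treatment effect in the model cannot be estimated.

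**Reading 2: usual-care tablets are counted as well.** Inputs:

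- 50 patients (9.2), each with 14 days per treatment (4.1), complete data assumed: 50 × 14 = 700 patient-days per treatment.
- Naloxegol: 1 tablet a day (8.1, Appendix D), so 7 a week.
- Senna: 1 to 8 tablets a day (1.1), so 7 to 56 a week.
- Bisacodyl: 4.4 equates 10–15 mg with 2–3 tablets, so 5 mg each. The 5–15 mg/day in 4.4 is 7 to 21 tablets a week; the 30 mg/day elsewhere is up to 42.

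Expected tablets = 700 × tablets due per day × adherence. With totals N (naloxegol) and U (usual care), the Poisson Wald statistic is z = ln(U/N) / √(1/N + 1/U). In a complete crossover this is the within-patient comparison. The adherence values are illustrative.

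| Usual-care tablets due/day | Adherence, naloxegol / usual care | N | U | U/N | z |
|---|---|---|---|---|---|
| 1 | 100% / 100% | 700 | 700 | 1.0 | 0 |
| 2 | 100% / 100% | 700 | 1,400 | 2.0 | 15.0 |
| 8 | 100% / 100% | 700 | 5,600 | 8.0 | 51.9 |
| 2 | 100% / 50% | 700 | 700 | 1.0 | 0 |
| 4 | 90% / 60% | 630 | 1,680 | 2.67 | 21.0 |
| 1 | 100% / 90% | 700 | 630 | 0.90 | −1.9 |

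For the second row: ln 2 / √(1/700 + 1/1,400) = 0.693 / 0.0463 = 15.0.

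Rows 2 and 3 show huge statistics with no compliance difference. Row 4 hides a 50-point gap. Row 5 points the wrong way: usual care has the worse adherence and the higher count. Row 6, a true 10-point gap with equal regimens, gives only |z| = 1.9. A usual-care mean of 1.11 tablets a day is enough to reject at an unadjusted 0.05: ln 1.11 / √(1/700 + 1/777) = 2.0.

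A simulation of 2,000 trials per setting, with 90% adherence on both treatments and the tablets due per day varying between patients, agrees. The test rejected every time when usual care was 1–2, 1–3 or 1–8 tablets a day (mean ratios 1.50, 2.00 and 4.51).

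Rescue use adds 1–3 doses × 2–3 tablets = 2 to 9 tablets per episode, on either treatment.

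**What the planned data can support.** Naloxegol adherence has a clear denominator. The 95% half-width is 1.96 × √[0.9 × 0.1 × (1 + 13ρ) / 700], where 90% adherence and the intra-patient correlation ρ are assumptions. It is 2.2 percentage points at ρ = 0, and 3.4, 4.9 and 6.1 points at ρ = 0.1, 0.3 and 0.5. The denominator must be doses due: a patient with a 3-day hold required by 4.6 would score 11/14 = 79% against 14 tablets, but 100% of doses due.

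**The case against.** The strongest defence is that 9.3.4 speaks of the effect of naloxegol on weekly pill counts, and that the protocol's rationale is the burden of titrating laxatives. Read as pill burden, a raw count is interpretable. That stands, and it is why the contrast need not be discarded if usual-care tablets really are counted. It does not rescue the present wording, which labels the endpoint compliance in 2.3, 2.4, 9.3.4 and the synopsis.

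A second defence is that the detailed procedures favour the naloxegol-only reading, under which no misleading p-value could arise. That is also fair. The z-values above belong only to the other reading, and a reader should not infer that the trial will produce such a result. The documents leave the matter open, because 4.1 and the Schedule of Events do not share the restriction.

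A reader might also infer that a rejection driven by regimen size would damage the Holm procedure by relaxing the threshold for the other endpoints. The documents do not support this. If tablet rates differ, that null hypothesis is false and rejecting it is correct, so family-wise error is still controlled. With K tests, such a rejection moves the next threshold from 0.05/K to 0.05/(K − 1), which is where removing the test also leads. K itself is not stated: 9.3.3 does not say whether adverse events are tested or whether the questionnaires are tested by item, domain or total.

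**Conclusion.** The point holds: on neither reading is the planned contrast an analysis of compliance. Either it has no usual-care data, or it compares regimen sizes. On the second reading the distortion is large (z = 15.0 at two usual-care tablets a day with equal adherence) and can run in either direction. The count tracks compliance only if every usual-care patient is due exactly one tablet a day and rescue tablets are left out.

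The first conclusion rests on the text alone. The sizes rest on 50 complete patients, Poisson variance and illustrative adherence values.

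The consequence is limited to the misreading of one exploratory result. The primary feasibility conclusion is untouched, and naloxegol compliance itself can be reported from the counts already planned. The change should be made, but the trial's main result does not depend on it.

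**What to change.** In both 9.3.4 and the synopsis, since changing only one would create a new contradiction:

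- Stop using the between-treatment pill-count test as the compliance analysis.
- Report naloxegol doses taken over doses due per patient, from tablets dispensed minus returned and checked against the Appendix D diary, with a confidence interval clustered by patient. Show protocol-required holds and early discontinuation separately, not as non-compliance.
- Describe usual-care and rescue laxative use from the medication use diary, which records doses taken, not doses prescribed.
- Drop the between-treatment contrast or, if usual-care tablets are in fact counted, keep it as a descriptive measure labelled pill burden. Either way, remove it from the Holm family and list the tests that remain.
- State which products are counted, and align 4.1 and the Schedule of Events with 5.1.13.1, 5.3.3 and 8.1.2.

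Separately, the bisacodyl range in 4.4 (5–15 mg/day) must be reconciled with the 30 mg/day ceiling in the synopsis and sections 1.1, 1.3 and 4.1. This review takes no position on which is right.

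The cost is plan and synopsis wording and minor analysis code. No new data are needed, and one exploratory contrast is lost as a test.

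As an optional minor note, the utilization analysis, planned as "fitting a Poisson regression model (or negative binomial in the case of over dispersion) of treatment arm on bi-weekly utilization count", could add a patient effect and a period term with allowance for residual dispersion, in line with 9.3.3, though any gain in power depends on rates that the documents do not give and may be small or slightly negative.

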	
Key Exclusion Criteria
 
 1. Patients receiving the following medications within 3 days of Study Day 1 and/or are planned to receive throughout the duration of the study period: opioid antagonist, mixed antagonist, a strong CYP3A4 and/or P-glycoprotein (P-gp) inhibitor, a moderate CYP3A4 and/or P-gp inhibitor, and/or a strong CYP3A4 inducer. 2. Patient currently receiving or planned to receive concurrent total parenteral nutrition. 3. Concurrent use of metoclopramide or use within 24 hours prior to study treatment (given elimination $t_{1/2}$ 6 hours). 4. Patients at high risk for bowel perforation. 5. Constipation that was not primarily caused by opioids in the investigator's medical opinion. 6. A condition that may have affected the permeability of the blood-brain barrier (e.g., known brain metastases, meningeal metastases, brain injury, multiple sclerosis, recent brain injury, uncontrolled epilepsy) 7. Patient has clinically active diverticular disease. 8. Past medical history of irritable bowel syndrome, signs of active gastrointestinal (GI) bleeding, acute surgical abdomen, bowel stents, indwelling peritoneal catheter, mechanical GI obstruction, fecal impaction, or fecal ostomy. 9. Patient has motility/neurologic disorders including autonomic failure (spinal cord lesions, tumor invasion of nerves) and/or poorly controlled endocrine/metabolic disorders (hypercalcemia, hypokalemia, diabetes, hypothyroidism), as determined by the investigator. 10. Uncontrolled cancer pain despite analgesic therapy 11. Pregnant or lactating female; men planning to father a child or women planning a pregnancy while taking study drug or within 28 days after the last dose of study drug
Study Product(s), Dose, Route, Regimen	Naloxegol (MOVANTIK™) is a round, bi-convex, white film-coated tablet. Subjects will receive 25 mg of naloxegol once daily, as an oral tablet (PO). Subjects will take naloxegol one hour before eating in the morning.
Duration of administration	Subjects will receive naloxegol or usual care for a 2-week initial treatment period followed by 3-day washout period, then a 2-week crossover treatment period where subjects will receive naloxegol or usual care. Treatment assignment during the initial and crossover treatment periods will be dictated by the randomization arm. Subjects will also have the option to participate in a 12-week extension phase of naloxegol.

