	
Safety endpoints will be evaluated by monitoring adverse events adverse events from clinical and laboratory reporting, using the NCI-CTCAE. Trends in the distribution and severity of adverse events across the study groups will be assessed by examining the count of total adverse events and count of adverse events at each severity level over the course of the 2 weeks for the initial treatment and over the 2 weeks of the crossover treatment phases of the study.
 
Secondary outcome measures are the effect of naloxegol versus usual care on; bowel movements per week, stool quality using the BSS,² occurrence and grade of adverse events using the NCI CTCAE version 4.03,³ health related quality of life utilizing the PAC-SYM⁴ & PAC-QOL,⁵ and changes in patient reported pain using the Brief Pain Inventory.⁶ For variables in the secondary aim, we plan to use generalized linear mixed effects models (GLM) to determine the impact of naloxegol on each endpoint over the course of 2 weeks for the initial treatment and crossover treatment phases of the study, achieved by treating the crossover arm as a time-dependent covariate. Within the GLM model; count of bowel movements per week will be assessed using a Poisson model. Stool quality (BSS, 7 point Likert-type scale), PAC-SYM (5 point Likert-scale), and PAC-QoL (5 point Likert-scale) will be assessed using an ordinal logistic model. The two parts of the BPI-sf (Intensity of pain and inference of pain) are calculated as the mean of several questions; as such they will be assessed as a continuous outcome with possible transformation for skewness if necessary. To control for the multiple comparisons a Bonferroni-Holm (e.g. Stepwise Bonferroni) method will be applied to the combined secondary and exploratory analyses, using an omnibus $\alpha = 0.05$.
 
Exploratory aims include laxative compliance (weekly pill counts), healthcare resource utilization (per electronic medical record evaluation of emergency room visits, hospitalizations, telephone encounters, and Mychart encounters), and patient preference (as evidenced by patient desire to continue naloxegol optional 12-week extension).
 
For analysis of differences in weekly pill counts between naloxegol and usual care, we plan to use a generalized linear mixed effects model to determine the impact of naloxegol on weekly pill counts, over the course of 2 weeks for the initial treatment and crossover treatment phases of the study, achieved by treating the arms as a time-dependent covariate. Within this model the weekly pill counts will be assessed using a Poisson model. Count of healthcare utilization resource, will be the sum of total utilizations (summed separately for each of the two weeks for initial treatment and cross over phase). Differences in healthcare utilization between the arms will be determined by fitting a Poisson regression model (or negative binomial in the case of over dispersion) of treatment arm on bi-weekly utilization count. We will examine patient preference by calculating a 95% confidence interval for the proportion of patients who wish to continue the optional 12-week extension.

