2.3 Exploratory Objectives

1. To evaluate laxative compliance with weekly pill counts.
2. To evaluate healthcare resource utilization as defined by the number of emergency room visits, hospitalizations, telephone encounters, and EPIC mychart encounters regarding signs/symptoms associated with constipation between the two arms.
3. To determine patient preference to continue naloxegol in the optional 12-week extension.

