4.2 Treatment Administration

Patients in Arm A will receive a single daily dose of 25mg naloxegol for the 2-week initial treatment period, followed by a 3-day washout period and 2-week crossover treatment period in which the patient will receive the treating physician's usual care for OIC using a stimulant laxative ± rescue medication.

Patients in Arm B will receive the treating physician's usual care for OIC using a stimulant laxative ± rescue medication for the 2-week initial treatment period, followed by a 3-day washout period and 2-week crossover period in which the patient will receive a single daily dose of 25mg naloxegol.

Patients on Arms A and B will have the option to continue on naloxegol at 25 mg daily for an additional 12-week extension phase upon completion of initial and crossover treatment phases.

Patients will be instructed to take naloxegol on an empty stomach at least 1 hour prior to the first meal of the day or 2 hours after the meal. Tablets must be swallowed whole, and not crushed or chewed by the subject. Subjects will also be instructed to avoid consumption of grapefruit or grapefruit juice as this is a potent inhibitor of the CYP3A4 enzyme.

Patients will also be instructed to complete a daily study drug diary during the treatment phases when naloxegol is being administered. Patients will be asked to bring their completed study drug diary with them during each visit for review with a member of the study team.

If the patient misses their daily morning dose of naloxegol and it has been less than 2 hours since the missed dose, they will be instructed to take naloxegol as soon as it is remembered on the same day. If it has been more than 2 hours since missing a dose, the patient will be instructed to skip the dose for that day not to make up that dose. If the patient vomits after taking a dose, he/she will be instructed not to repeat the dose or attempt to make up that dose.

If a patient takes more than the assigned daily dose of naloxegol, they should be monitored closely for evidence of opioid withdrawal symptoms and reversal of central analgesic effects. In cases of known or suspected overdose, symptomatic treatment as well as monitoring of vital functions should be performed. In cases of severe intoxication, intensive care procedures are recommended. Close medical supervision and monitoring should be continued until the patient recovers.

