9.3.3 Secondary Endpoints

Secondary outcome measures are the effect of naloxegol versus usual care on; bowel movements per week, stool quality using the BSS,² occurrence and grade of AEs using the NCI CTCAE version 4.03,³ health related quality of life utilizing the PAC-SYM⁴ & PAC-QoL,⁵ and changes in patient reported pain using the BPI-sf.⁶

For variables in the secondary aim, we plan to use generalized linear mixed effects models to determine the impact of naloxegol on each endpoint over the course of 2 weeks for the initial treatment and crossover treatment phases of the study, achieved by including treatment group as a categorical covariate, and including a categorical time effect to account for a potential period effect. Counts of bowel movements per week will be assessed using a Poisson model. Stool quality (BSS, 7 point Likert-type scale), PAC-SYM (5 point Likert-scale), and PAC-QOL (5 point Likert-scale) will be assessed using an ordinal logistic model. The two parts of the BPI-sf (Intensity of pain and inference of pain) are calculated as the mean of several questions; as such they will be assessed as a continuous outcome with possible transformation for skewness if necessary.

To control for the multiple comparisons, a Bonferroni-Holm (e.g. Stepwise Bonferroni) method will be applied to the combined secondary and exploratory analyses, using an omnibus $\alpha = 0.05$.

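### The health-care utilization model names treatment arm as its only term: as sequence it does not estimate naloxegol versus usual care, and as treatment received it still lacks period and patient terms

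*Combined protocol and SAP*

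**What the plan says.** Section 9.3.4 sets the utilization analysis: "Differences in healthcare utilization between the arms will be determined by fitting a Poisson regression model", or a negative binomial model if the counts are over-dispersed. The regression is "of treatment arm on bi-weekly utilization count". Counts are "summed separately for each of the two weeks for initial treatment and cross over phase". No period term, patient effect or coding of arm by period is named, and the Statistical Methodology entry of the Study Summary gives the same model. Exploratory Objective 2 in section 2.3 is phrased the same way: "EPIC mychart encounters regarding signs/symptoms associated with constipation between the two arms".

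The design sections make the arms sequences. Section 4.2 says "Patients in Arm A will receive a single daily dose of 25mg naloxegol for the 2-week initial treatment period", followed by washout and usual care; Arm B takes the reverse order. The Study Summary adds: "Treatment assignment during the initial and crossover treatment periods will be dictated by the randomization arm".

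The neighbouring models are more fully specified. The secondary endpoints in 9.3.3 get mixed models with treatment group as a covariate, "including a categorical time effect to account for a potential period effect". Pill counts in 9.3.4 get a Poisson mixed model that explicitly compares naloxegol with usual care, and the synopsis says of that model that it is "achieved by treating the arms as a time-dependent covariate".

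**The concern.** In a two-sequence crossover every patient is planned to receive both treatments, so a comparison of the randomised arms compares orders of treatment. Each arm's pooled count is part naloxegol and part usual care. An analyst who codes the covariate from the randomisation list would report a ratio near 1 largely regardless of what naloxegol does, and it could be read as no effect on emergency visits, admissions and calls.

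Coding the covariate as treatment received avoids that, but the model would still treat a patient's two counts as independent and ignore any drift between periods. The p-value also matters beyond its own endpoint, because 9.3.3 puts secondary and exploratory tests into one Holm procedure at an overall 0.05.

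**Working it through.** **The plan's own figure.** The documents give no design figure for utilization. The only one is the power of the primary test (section 9.2: 50 patients, 70% versus 85%, one-sided exact 0.05). The critical value is 41 of 50, with exact size 0.0402 and power 0.791 against the stated 80%. It reproduces and is not affected by this point.

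**Inputs.** From the documents: 1:1 allocation, 50 treated patients (so 25 per sequence), and two 2-week periods. Assumed, because the documents give none: usual-care rate λ per 2 weeks, naloxegol/usual care ratio RR, period 2/period 1 ratio π, and between-patient (gamma frailty) variance.

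**Expected counts per patient.**

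| | Period 1 | Period 2 |
|---|---|---|
| Arm A | λ·RR | λ·π |
| Arm B | λ | λ·π·RR |

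**Reading 1: arm is the sequence, periods pooled.** A/B = (λ·RR + λ·π)/(λ + λ·π·RR) = (RR + π)/(1 + π·RR). The rate λ drops out.
- π = 1: (RR + 1)/(1 + RR) = 1.00 for any RR.
- π = 0.8, RR = 0.5: 1.3/1.4 = 0.93.
- π = 0.8, RR = 0.7: 1.5/1.56 = 0.96.

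**Reading 2: Arm A versus Arm B within each period.** Period 1 gives RR and period 2 gives λ·π/(λ·π·RR) = 1/RR. At RR = 0.5 these are 0.5 and 2.0. The effect can be recovered, but with opposite signs and from between-patient tests.

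**Reading 3: arm is the treatment received.** Naloxegol/usual care = (λ·RR + λ·π·RR)/(λ + λ·π) = RR. Nothing cancels while the periods are balanced.

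**Simulation of the tests.** 25 per sequence, λ = 1, π = 1.0 or 0.8, variance near 0 (0.01) or 1, two-sided 5%, 1,500 runs per setting:

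| Model | Rejection at RR 0.5 | Rejection at RR 1 |
|---|---|---|
| Sequence, plain Poisson, variance near 0 | 5–6% | 5% |
| Sequence, plain Poisson, variance 1 | 20–21% | 25% |
| Arm within one period, plain Poisson (both variances) | 39–53% | 5–18% |
| Treatment received, plain Poisson (both variances) | 79–83% | 4–6% |
| Within-patient, period-adjusted (both variances) | 78–83% | 4–6% |

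In the second row the sequence model rejects at least as often with no drug effect as with a halving. That is unmodelled between-patient variation, not signal.

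**The fallback.** With λ = 1 and frailty variance 1, a usual-care count has variance λ + λ² = 2, twice the Poisson value, so the plan's over-dispersion clause would be expected to apply. A separate simulation at those values (25 per arm) fitted the negative binomial model on treatment received with no patient effect. It rejected about 0.5% under no effect and had about 65% power at RR 0.5, against about 85% for treatment received with a period term and patient clustering. The fallback charges stable differences between patients as noise against a contrast that is made within patients. A repeat at the same settings agreed to within a few percentage points.

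**The case against.** The strongest reply is that the documents often use arm to mean a treatment. Sections 4.4 and 4.5 speak of usual care as an arm. The synopsis has the arms varying over time in the pill-count model, shortly before the utilization sentence, and a randomised sequence cannot vary over time. The sequences themselves are usually called Arm A and Arm B or the randomization arm, whereas 9.3.4 says treatment arm. Keeping counts separate by phase also fits a per-period treatment covariate. On that usage, both the objective and the analysis mean naloxegol versus usual care.

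This stands as far as it goes: the sequence contrast is one reading, not the only one. It does not settle the matter. The synopsis states the time-varying coding for pill counts and omits it for utilization, and 9.3.4 moves from naloxegol versus usual care for pill counts to the arms for utilization. The benign reading also leaves the period and patient terms absent.

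Two further replies have weight. With 1:1 allocation, treatment and period are balanced by design, so the missing period term biases the treatment-received ratio only if loss between periods differs by sequence; no figures allow that to be sized. And a plain Poisson model on treatment received kept its size in the simulation (4–6%). The loss shown above comes with the negative binomial fallback.

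**Conclusion.** The covariate is ambiguous and the model under-specified. As the randomised arm with periods pooled, the contrast does not estimate naloxegol versus usual care: 1.00 without a period effect, and 0.93 at RR 0.5 and π 0.8. As treatment received, it targets the right ratio, but its standard errors can be wrong: with the fallback, about 0.5% rejection under no effect and 65% power instead of 85%. The algebra for the ratios does not depend on λ. The rejection rates rest on assumed values for contact rate, effect and between-patient variance, and with little between-patient variation the error-rate problem largely disappears.

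A reader might infer that the plan necessarily cancels the naloxegol effect and cannot answer its objective. The documents do not support that. Cancellation requires sequence coding and pooling of both periods, neither of which is stated outright; it is exact only without a period effect; and the data, collected by phase, can answer the question. The endpoint is exploratory, so the primary conclusion and sample size are untouched. The reach beyond it is through the Holm family in 9.3.3.

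**What to change.** In section 9.3.4, the synopsis and Exploratory Objective 2 (section 2.3 and the Study Summary), state the comparison as naloxegol versus usual care. In the two statements of the model:

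- Define the covariate as the treatment received in each 2-week period.
- Add the categorical period effect already used in 9.3.3.
- Add a patient random effect, or use patient-clustered standard errors.
- Keep the negative binomial option, with the same patient-level handling.

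The cost is the wording of one model and one objective. No new data, visits or patients are needed.
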